- During Screening (Visit 1) and Dosing (Visit 3), only one IOP timepoint in the morning is needed (see Section 12 for specific time window).
- During Day 2 (Visit 4) and Day 28 (Visit 5a), only the 8 a.m. IOP timepoint is needed. Day 14 (Visits 5) and Day 42 (Visit 6) require full diurnal evaluation.
- Lab and PK samples were not collected at Day 2 (Visit 4) and Day 28 (Visit 5a). Pregnancy test is only required at Day 14 (Visit 5).
- Timolol maleate 0.5% ophthalmic solution is given to the patient to take their first dose in the non-study eye the evening of the their Day 1 Dosing (Visit 3) then dose BID for the remaining portion of the study. Patients will be instructed to return their used bottle(s) at each visit for accountability purposes. A new supply of timolol maleate 0.5% ophthalmic solution will be provided on a monthly basis starting at Day 42 (Visit 6) through Month 11 (Visit 15). During post dose study visits, ensure Timolol maleate 0.5% ophthalmic solution is administered after the 8 AM IOP measurement.
- ⁷ Gonioscopy photographs are not collected at Day 2 (Visit 4).
- V16/Month 12 Time and Events Schedule should only be used if patients are not continuing into the Cohort 2 Study Extension 1 and plan to exit the study at V16/Month 12. If the patient is continuing into the Cohort 2 Study Extension 1, V16/Month 12 should follow the Time and Events Schedule in the Cohort 2 Study Extension 1 Synopsis, Table 3.

Specular microscopy is needed for all study eyes on all indicated visits; for non-study eyes, it is collected only during Screening (Visit 1) and Exit/Early Exit (Visit 16). Additional measurements may be taken at the investigator's discretion.

ENV515-01 PHASE 2A CLINICAL STUDY, COHORT 2 EXTENSION 1

Cohort 2 Extension 1 Protocol Synopsis

Investigational Product: ENV515-3 (Travoprost) Intracameral Implant

Phase: 2a Cohort 2 Extension 1

Cohort 2 Study Extension 1 Objective:

• Extend the ENV515-01 Ph2a Cohort 2 study duration beyond 12 months by an additional 6 months to continue evaluation of the ENV515-3 long term safety, efficacy, and biodissolution in patients with bilateral ocular hypertension or primary open-angle glaucoma

Clinical Hypotheses:

 A single dose of two ENV515-3 (travoprost) Intracameral Implants will demonstrate end of duration of IOP treatment effect and full biodissolution in the time period between 13 and 18 months

Cohort 2 Study Extension 1 Design:

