- Change from baseline in time-matched 8 AM IOP measurements at Months 13, 14, 15, 16, 17 and 18 for study and non-study eye
- Percent change from baseline in time-matched 8 AM IOP measurements for study eye and non-study at Months 13, 14, 15, 16, 17 and 18
- Difference in change from baseline and percent change from baseline in time-matched 8 AM IOP measurements between study eye and non-study eye at all study time points and visits
- Cumulative % of study and non-study eyes with at least 20, 25, and 30% reduction in 8 AM IOP at all study time points and visits
- Cumulative % of patients with 8 AM IOP <18 at all time points at each study visit
- Mean 8 AM IOP at all visits all time points

Safety Measures: Assessed by evaluating changes from baseline in the following:

- Specular microscopy (non-contact)
- Slit-lamp biomicroscopy
- Corneal staining
- Dilated fundus examination
- Gonioscopy exam
- Anterior chamber OCT exam
- Pupil measurement
- Pachymetry (contact)
- BCVA (ETDRS)
- Visual Field
- Body system assessment
- Vital signs
- Non fasting clinical laboratory tests (chemistry, hematology, urinalysis)
- Urine pregnancy tests for females of childbearing potential
- AEs

Table 3: Time and Events Schedule, Cohort 2 Extension 1, Months 12 to 18, Including New Schedule for Month 12 Visit for Patients Enrolled in the Cohort 2 Extension 1

Note: If the patient is continuing into the Cohort 2 Study Extension 2, V22/Month 18 should follow the Time and Events Schedule in the Cohort 2 Study Extension 2 Synopsis, Table 4.

Procedure	Treatment V16 Month 12 +/- 7 days	Treatment V17 Month 13 +/- 7 days	Treatment V18 Month 14 +/- 7 days	Treatment V19 Month 15 +/- 7 days	Treatment V20 Month 16 +/- 7 days	Treatment V21 Month 17 +/- 7 days	Exit/Early Exit ⁴ V22 Month 18 +/- 7 days
Informed consent review	X						
Concomitant medication query	X	X	X	X	X	X	X
Adverse events query	X	X	X	X	X	X	X
BCVA – (ETDRS)	X	X	X	X	X	X	X
Pupil measurement	X		X		X		X
Slit-lamp biomicroscopy	X	X	X	X	X	X	X
Corneal staining	X	X	X	X	X	X	X
Gonioscopy	X	X	X	X	X	X	X
Gonioscopy photographs (at selected sites)	X	X	X	X	X	X	X
Pachymetry	X		X		X		X
Specular microscopy	X^1		X^1		X^1	X^1	X^1
Visual field							X
Anterior chamber OCT ³	X					X	X
8 AM IOP	X	X	X	X	X	X	
IOP diurnal curve							X
Dilated fundus exam	X						X
Body System Assessment	X						X
Vitals	X			X			X
Hematology, chemistry and urinalysis	X						X
Plasma collection for PK analyses							X
Urine Pregnancy test							X

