Timolol maleate 0.5% distribution and collection ²	X	X	X	X	X	X	X
Exit patient, complete exit form							X

- Specular microscopy is needed for all study eyes on all indicated visits; for non-study eyes, it is collected only during Exit/Early Exit (Visit 22). Additional measurements may be taken at the investigator's discretion.
- Timolol maleate 0.5% ophthalmic solution is given to the patient to continue dosing BID for the remainder of the study. Patients will be instructed to return their used bottle(s) at each visit for accountability purposes. A new supply of timolol maleate 0.5% ophthalmic solution will be provided on a monthly basis through Month 17 (Visit 21). During post dose study visits, ensure timolol maleate 0.5% ophthalmic solution is administered after the 8 AM IOP measurement.
- Always capture the ENV515 implant(s) in the field of view of at least one OCT image.
- V16/Month 12 Time and Events Schedule should only be used if patients are continuing into the Cohort 2 Study Extension 1. If the patients are continuing into the Cohort 2 Study Extension 2, V22/Month 18 should follow the Time and Events Schedule in the Cohort 2 Study Extension 2 Synopsis, Table 4.

ENV515-01 PHASE 2A CLINICAL STUDY, COHORT 2 EXTENSION 2

Cohort 2 Extension 2 Protocol Synopsis

Investigational Product: ENV515-3 (Travoprost) Intracameral Implant

Phase: 2a Cohort 2 Extension 2

Cohort 2 Study Extension 2 Objective:

• Extend the ENV515-01 Ph2a Cohort 2 study duration beyond 18 months (12 month Cohort 2 + 6 month Extension 1) by an additional 3 months in Extension 2 to continue evaluation of the ENV515-3 long term safety, efficacy, and biodissolution in patients with bilateral ocular hypertension or primary open-angle glaucoma

Clinical Hypotheses:

 A single dose of two ENV515-3 (travoprost) Intracameral Implants will demonstrate end of duration of IOP treatment effect and full biodissolution in the time period between 13 and 21 months

Cohort 2 Study Extension 2 Design:

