Cohort 2 Study Extension 2 Visit Schedule: Visit schedule encompasses Treatment Visits 23 and 24 (Months 19 and 20) and Exit Visit 25 (Month 21). Patients may be exited sooner than Month 21 if they have received rescue therapy, their IOP in the study eye is well-controlled, no implant remnants are visible by gonioscopy during two consecutive visits, and no treatment related adverse events (AEs) are present that require continued monitoring.

Response Measures in Cohort 2 Study Extension 2 (Month 18 to 21):

Exploratory Efficacy Measure:

- Change from baseline in time-matched 8 AM IOP measurements at Months 19, 20 and 21 for study and non-study eye
- Percent change from baseline in time-matched 8 AM IOP measurements for study eye and non-study at Months 19, 20, and 21
- Difference in change from baseline and percent change from baseline in time-matched 8 AM IOP measurements between study eye and non-study eye at all study time points and visits
- Cumulative % of study and non-study eyes with at least 20, 25, and 30% reduction in 8 AM IOP at all study time points and visits
- Cumulative % of patients with 8 AM IOP <18 at all time points at each study visit
- Mean 8 AM IOP at all visits all time points

Safety Measures: Assessed by evaluating changes from baseline in the following:

- Specular microscopy (non-contact)
- Slit-lamp biomicroscopy
- Corneal staining
- Dilated fundus examination
- Gonioscopy exam
- Anterior chamber OCT exam
- Pupil measurement
- Pachymetry (contact)
- BCVA (ETDRS)
- Visual Field
- Body system assessment
- Vital signs
- Non fasting clinical laboratory tests (chemistry, hematology, urinalysis)
- Urine pregnancy tests for females of childbearing potential
- AEs

Table 4: Time and Events Schedule, Cohort 2 Study Extension 2, Months 18 to 21, Including New Schedule for Month 18 Visit for Patients Enrolled in the Extension 2

Procedure	Treatment V22 Month 18 +/- 7 days	Treatment V23 Month 19 +/- 7 days	Treatment V24 Month 20 +/- 7 days	Exit/Early Exit V25 Month 21 +/- 7 days
Informed consent review	X			
Concomitant medication query	X	X	X	X
Adverse events query	X	X	X	X
BCVA – (ETDRS)	X	X	X	X
Pupil measurement	X	X	X	X
Slit-lamp biomicroscopy	X	X	X	X
Corneal staining	X	X	X	X
Gonioscopy	X	X	X	X
Gonioscopy photographs (at selected sites)	X	X	X	X
Pachymetry	X	X	X	X
Specular microscopy	X ¹	X ¹	X^1	X ¹
Visual field				X
Anterior chamber OCT ³	X	X	X	X
8 AM IOP	X	X	X	
IOP diurnal curve				X
Dilated fundus exam				X
Body System Assessment				X

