In the event that study discontinuation and withdrawal of a subject is necessary, the investigator should make every attempt to complete all protocol safety assessments and visits. Unless consent has been withdrawn, any subject is considered to be in the treatment phase of the study until the completion of the study, and such subjects should continue to be followed and will be expected to complete all safety assessments and visits.

11.8. Early Exit Criteria, Cohorts 2 and 3

Patients may also exit the study sooner than their exit visit if all of the following are true:

- They have received rescue therapy
- Their IOP in the study eye is well controlled
- No implant remnants are visible by gonioscopy on two consecutive visits
- No treatment related adverse events are present that require continued monitoring.

Communication

12. PROCEDURE SCHEDULE BY STUDY VISIT, COHORT 2

12.1. Visit 1/-49 to -29 days/Screening Evaluation, Cohort 2

At Visit 1, patients will be screened, and if eligible, enrolled into the study. Before any study specific assessments are performed, written informed consent will be obtained from each patient. Screening procedures can be conducted over several visits but should be completed within a 7 day period. During the visit, the procedures described below will be performed.

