2. PROTOCOL SUMMARY

ENV515-01 is a multicenter, open-label, prospective, active-comparator-controlled Phase 2a study of ENV515 (travoprost) Intracameral Implant comprising three stages:

- The completed Cohort 1 was a 28-day study focused on evaluation of the initial safety, efficacy, and pharmacokinetic properties of ENV515 conducted in glaucoma patients scheduled for cataract removal during which the ENV515 implant is removed during the cataract procedure 28 days after implantation. This cohort was covered in a separate SAP and no further mention of this cohort will be made in this SAP.
- Cohort 2 is a 12-month study with a 6-month optional Extension 1 followed by an additional 3-month optional Extension 2 (for a total of up to 21 months) that is focused on evaluation of the long-term safety and efficacy in glaucoma patients during which the two ENV515-3 implants are followed through their biodissolution while the duration of intraocular pressure (IOP)-lowering efficacy is assessed.
- Cohort 3 is a 12-month study with a 6-month optional Extension 1 followed by an additional 6-month optional Extension 2 (for a total of up to 24 months) that is focused on evaluation of the long-term safety in glaucoma patients during which one or two ENV515-3-2 implants per study eye are followed through their biodissolution.

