8. EFFICACY EVALUATION

8.1 Primary Efficacy Analysis

The primary efficacy endpoint for this study is the change from baseline in time-matched IOP measurements for the study and non-study eye. Intraocular pressure is collected at 8 am. Values for IOP and change from baseline will be summarized by visit and time, cohort dose group, and eye as specified in Section 3. Baseline will be defined as the last IOP measurement prior to implantation and will be time-matched. No formal statistical testing will be done.

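### Both Cohort 2 extensions hypothesise when the IOP effect ends, but nothing defines the end of effect and the planned by-visit IOP table cannot date or count it

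*Protocol*

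**What the plan says.** Each Cohort 2 extension has one clinical hypothesis. Extension 1: two implants "will demonstrate end of duration of IOP treatment effect and full biodissolution in the time period between 13 and 18 months". Extension 2 repeats it with a wider window: "will demonstrate end of duration of IOP treatment effect and full biodissolution in the time period between 13 and 21 months".

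The extension IOP measures are labelled exploratory and organised by visit: "Change from baseline in time-matched 8 AM IOP measurements at Months 13, 14, 15, 16, 17 and 18 for study and non-study eye" in Extension 1 and "Change from baseline in time-matched 8 AM IOP measurements at Months 19, 20 and 21 for study and non-study eye" in Extension 2. Percent change, between-eye difference, the share of eyes with at least 20, 25 or 30% reduction, the share with IOP below 18, and mean IOP accompany them. None states when an eye's effect has ended.

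The 2019 SAP (Cohorts 2 and 3), Section 2, says the Cohort 2 implants are followed through dissolution "while the duration of intraocular pressure (IOP)-lowering efficacy is assessed". Its IOP analysis in Section 8.1 is: "Values for IOP and change from baseline will be summarized by visit and time", with no formal testing. Section 3 sets the statistics (mean, SD, minimum, maximum, median, n). Section 10 drops all secondary summaries, and Section 11 lists a single IOP table, 14.2.1. Section 12 lists IOP, prior and concomitant medications, and disposition. Section 9.2 summarises days from insertion to implant dissolution or removal.

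**The concern.** When the effect ends is a question about each eye's time to loss of effect. The biodissolution half of the hypothesis has a matching per-patient duration in SAP 9.2, but the IOP half has none. The responder percentages come closest, and the SAP gives them no table.

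Two features of the protocol make late by-visit values a poor substitute. Section 11.6 makes rescue permanent when it is needed after 7 months, which covers the whole of Months 13 to 21, and SAP 8.1 has no rule for readings on rescue. Section 11.8 lets patients leave early if four conditions are all met, the first being "They have received rescue therapy", so some rescued eyes may drop out of later visits. A late visit value can therefore reflect rescue drug or a selected subset.

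At stake is whether the study can say in how many of at most 5 eyes the implant effect ended, and when. Without that, nothing shows whether the move from 18 to 21 months was borne out.

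**Working it through.** The plan gives no event count, power or precision for end of effect, so there is no figure to reproduce. The checks below show what the planned table can and cannot tell apart. Trajectories and rescue effects are assumed.

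**Inputs.** Cohort 1, Day 25, same dose (protocol 1.4.2): -5.1 mmHg (SD 1.7), -21.3% (SD 8.3%), n=7. Implied baseline 5.1/0.213 = 23.9 mmHg, so a 20% reduction is 0.20 × 23.9 = 4.8 mmHg. Number of eyes: up to 5 (extension synopses).

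**1. Same means, different answers.** Pattern A: five eyes hold -5.1 mmHg and lose it abruptly at Months 14, 15, 17, 18 and 20. Visit mean = -5.1 × (eyes with effect)/5. Rescue rows assume permanent rescue from the second month after loss.

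| Month | 13 | 14 | 15 | 16 | 17 | 18 | 19 | 20 | 21 |
|---|---|---|---|---|---|---|---|---|---|
| Eyes with effect | 5 | 4 | 3 | 3 | 2 | 1 | 1 | 0 | 0 |
| Mean, no rescue | -5.10 | -4.08 | -3.06 | -3.06 | -2.04 | -1.02 | -1.02 | 0 | 0 |
| Mean, rescue worth 3 mmHg | -5.10 | -4.08 | -3.06 | -3.66 | -3.24 | -2.22 | -2.82 | -2.40 | -2.40 |
| Mean, rescue worth 5.1 mmHg | -5.10 | -4.08 | -3.06 | -4.08 | -4.08 | -3.06 | -4.08 | -4.08 | -4.08 |

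Pattern B: all five eyes wane together along the no-rescue row. Apply one rule to both: first of two consecutive visits with less than 4.8 mmHg reduction. Pattern A ends at 14, 15, 17, 18 and 20, so 4 of 5 fall within 13-18 months and 5 of 5 within 13-21. Pattern B ends at Month 14 in every eye, so 5 of 5 fall within 13-18. The means are identical and the answers to the Extension 1 hypothesis differ. SD and range would separate these two patterns but would not by themselves date each eye.

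**2. Rescue hides the end.** At Month 21 in Pattern A, four eyes are on rescue and the fifth (lost at 20) is not yet. Mean = 4 × (-3)/5 = -2.4, or 4 × (-5.1)/5 = -4.1 mmHg. The implant-only value is 0.

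**3. The threshold matters.** With mean reduction 21.3% and SD 8.3%, assuming normality, the share of eyes already below a threshold at Day 25 is:
- 20%: Φ((20 - 21.3)/8.3) = 0.44
- 25%: Φ((25 - 21.3)/8.3) = 0.67
- 30%: Φ((30 - 21.3)/8.3) = 0.85

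These are diurnal averages in 7 eyes, so they are only a guide to 8 AM values. A threshold chosen after seeing the data could decide the result. A bare 20% rule would also confuse a weak responder with an eye whose effect has ended.

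**4. Precision if the gap is closed.** Exact 95% limits for k of 5 eyes ending in the window: 5/5, 47.8-100%; 4/5, 28.4-99.5%; 3/5, 14.7-94.7%.

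**The case against.** The strongest reply is that five eyes need no special analysis. The table gives range and n as well as means. The listings give every IOP value and disposition, and protocol 16.2.1 requires start and stop dates for medications, so rescue can be read against each eye's pressures. The extension measures are exploratory, the Cohort 2 and 3 objective is safety and tolerability, and the SAP openly serves an abbreviated report because the IND is being withdrawn. All of this stands and limits the weight of the point. It does not supply the missing rule, and SAP Section 10 does not say that the extension hypothesis will go unanswered.

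Some stronger readings go beyond the documents:
- A reader might infer that patients who lose effect are removed from later visits. Section 11.8 only permits exit, and requires all four conditions: rescue, controlled study-eye IOP, no visible remnants on two consecutive visits, and no treatment-related event needing monitoring. Many rescued eyes may stay. The extensions are also optional, so patients can leave at Month 12 or 18 with effect intact, and the direction of selection is not fixed.
- A reader might compute a mean that counts exited eyes at zero change. Early exit requires controlled pressure, so the plan would not observe that value, and no document figure supports any particular split of eyes.
- A reader might extend the criticism to Cohort 3. Its design text mentions duration, but its hypotheses concern safety only and its synopses list no efficacy measures.

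**Conclusion.** The point holds and should be acted on, at moderate weight. Following the plan exactly leaves the only hypothesis of each extension without a defined result for its IOP half, and late by-visit values can show continued lowering that comes from rescue drug. The size of that masking, 2.4 to 4.1 mmHg at Month 21 in the example, rests on assumed trajectories and an assumed rescue effect of 3 to 5.1 mmHg. The documents do not show that it occurred.

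It would be too strong to say the data contain no information on when effect ended: with at most 5 eyes the listings allow each one to be traced. What is missing is a pre-stated rule that makes the tracing reproducible, and an output that reports it.

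**What to change.** In the Cohort 2 part of the 2019 SAP, add one table and one listing giving days from implantation to loss of effect for each study eye.

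- **Definition (analysis only).** For example, the first of two consecutive scheduled visits with less than 20% reduction from the time-matched 8 AM baseline, counted only after the eye has first reached that reduction. Report eyes that never reach it separately. Repeat at another protocol responder level as a sensitivity check.
- **Rescue.** Count first rescue as an event, and also show it separately with its date, so a reader can see which ends rest on rescue alone. Censor at the last implant-only visit. The Cohort 2 synopses tie rescue to a change below 20% on two visits, while Section 11.6 ties it to the investigator's opinion. These passages must be reconciled before rescue is used as an event; no view is taken here on which is right.
- **Output.** Number of eyes ending before, within and after 13-18 and 13-21 months. Kaplan-Meier is optional at this size. Cohort 3 need not be included.
- **By-visit table.** Flag or separate post-rescue readings.

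The cost is SAP wording, one table and one listing from data already collected. The downside is that the result is descriptive and imprecise, as the limits above show.

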ENV515-3-2	Envisia Therapeutics designation for Intracameral Implant containi 26.1 µg travoprost		
ETDRS	Early Treatment of Diabetic Retinopathy Study		
GCP	Good Clinical Practice		
GLP	Good Laboratory Practice		
ICF	Informed Consent Form		
ICH	International Conference on Harmonisation of Technical Requirements for Registration of Pharmaceuticals for Human Use		
IOL	Intraocular Lens		
IOP	Intraocular Pressure		
IRB	Institutional Review Board		
ITT	Intent-To-Treat		
LogMAR	Logarithm of the Minimum Angle of Resolution		
MD	Mean Defect (as in visual field test)		
MedDRA	Medical Dictionary for Regulatory Activities		
MIG	Minimally Invasive Glaucoma implants		
NOAEL	No-Observed Adverse Effect Level		

Abbreviation or Specialist Term	Explanation		
NSE	Non-Study Eye		
OCT	Optical Coherence Tomography		
PGA	Prostaglandin Analogue		
PK	Pharmacokinetic(s)		
PLA	poly(D,L-lactide)		
PLGA	poly(lactic-co-glycolic acid)		
RGP	Rigid Gas Permeable (lenses)		
RPE	Retinal Pigment Epithelium		
SAE	Serious Adverse Event		
SE	Study Eye		
SITA	Swedish Interactive Threshold Algorithms		
SOP	Standard Operating Procedures		
SLT	Selective Laser Trabeculoplasty		
TBD	To Be Determined		
TM	Trabecular Meshwork		
VA	Visual Acuity		
VF	Visual Field		

1. INTRODUCTION

Glaucoma is a progressive optic neuropathy affecting more than 3 million Americans over the age of 39 and is a leading cause of blindness in adults over age 60. According to the National Eye Institute, more than 120,000 Americans are blind due to glaucoma (3, 4). Elevated intraocular pressure (IOP) is the most important risk factor for the development of glaucoma and is a result of abnormally high resistance to aqueous humor drainage through the trabecular meshwork (TM), a multi-laminar array of collagen beams covered by endothelial-like cells.

Due to limited understanding of the pathophysiology of the optic neuropathy characteristic of glaucoma, current glaucoma therapies are focused on reducing IOP. The prostaglandin analogues (PGAs) are currently the most prescribed class of topical therapies for ocular hypertension or glaucoma in the United States, with latanoprost, travoprost, and bimatoprost being used most frequently. However, their use has been limited by several shortcomings.

First, the compliance with existing glaucoma topical therapies is generally low, with 30% to 60% of patients discontinuing the therapy within the first year of treatment. Second, topical ophthalmic agents currently in use have local and systemic side effects (e.g., a relatively high incidence of hyperemia for topical PGAs, including travoprost). Third, the once a day administration of PGAs, accompanied by drug level peaks and troughs in the aqueous humor and the surrounding tissues, potentially leads to 24-hour IOP fluctuations that may contribute to accelerated loss of visual field (VF) in susceptible patients (5). Lastly, the combination of these factors has been shown to increase the cost of patient care due to more rapid disease progression.

Therefore, an alternative treatment using an extended-release delivery system with an improved safety/efficacy profile would be a welcome addition to the current pharmacological armamentarium. To date, there are no approved anti-glaucoma therapies that provide an extended-release of a pharmacological agent directly to the site of action. Development of an extended-release PGA formulation administered directly into the anterior chamber would likely improve both compliance and the adverse event (AE) profile of current PGA and other IOP lowering therapies.

ENV515 (travoprost) Intracameral Implant is a biodegradable, extended-release formulation containing travoprost (1, 2) in a poly(D,L-lactide) (PLA) biodegradable polymer drug delivery system. Studies in preclinical models with ENV515 formulations have shown sustained IOP lowering efficacy lasting up to 8 months following a single dose, combined with acceptable safety and tolerability profiles. This body of knowledge, pointing to a potential for improved compliance, ocular surface tolerability, and possibly long-term beneficial outcomes, makes ENV515 extended-release travoprost therapy a promising area of research and development.

